For at least 30 minutes after administration, patients should avoid lying in a supine position and taking food, drink (except for water) or other oral drugs.

4. Number of study sites to be surveyed by departments

This is an all-case surveillance and the number of sites is not determined irrespective of department.

5. Survey method

(1) Request to medical institutions and conclusion of contract

i) When requesting the surveillance, sufficient explanation on the summary and objective of this surveillance should be given to an investigator based on the “Request for Benet 17.5 mg Tablets Special Drug Use Surveillance in Patients With Osseous Paget's Disease (All-case Surveillance)”, “Guide for Benet 17.5 mg Tablets Special Drug Use Surveillance in Patients With Osseous Paget's Disease (All-case Surveillance)”, “Case Report Form for Benet 17.5 mg Tablets Special Drug Use Surveillance in Patients With Osseous Paget's Disease (All-case Surveillance) (sample)”.

ii) An agreement will be concluded with a medical institution cooperating this surveillance, and surveillance will be requested in all patients with osseous Paget's disease who receive this drug during the specified survey period.

(2) Enrollment of targeted patients

The investigator will enroll patients for “all-case registration” according to the following procedures.

i) The investigator will enroll all patients with osseous Paget's disease who receive this drug packaged for osseous Paget's disease after the date of marketing on and after the date of concluding an agreement and within 14 days from the date of starting administration as best as possible.

A patient who was previously enrolled in this survey at the concerned site will be enrolled again when this drug is re-administered.

*Staff of Takeda should pay sufficient attention to the use state of packaging for osseous Paget's disease and promptly request for enrollment when a use is confirmed.

ii) The investigator will record the necessary items in the “patient enrollment information” section on the cover page of CRF for all patients administered this drug during the survey period, cut off a duplicate post card (enrollment postcard) bound in the back page, cover with a masking tape, and post it to the enrollment center within 14 days as best as possible from

the baseline.

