To observe the efficacy and safety of BENET Tablets 17.5 mg/Actonel Tablet 17.5 mg in patients with osseous Paget's disease up to Week 48 as an all-case surveillance based on the approval conditions.

2. Patients to be included in analyses

(1) Breakdown of patients to be included in analyses

“Patients included in safety evaluation” and “patients included in efficacy evaluation”.

(2) Patients included in safety evaluation

Of the patients from whom a case report form (CRF) is collected, those who satisfy either of the following conditions are excluded from safety evaluation and others are included in safety evaluation.

- i) A patient not administered this drug
- ii) A patient in whom onset of adverse event is unknown
- iii) Of the patients with duplicated enrollment, those who were enrolled later.
- iv) A patient for whom administration was started outside the enrollment period*

* The date of starting administration falls after the enrollment period of January 31, 2016 (on and after February 1, 2016).

(3) Patients included in efficacy evaluation

Of the patients included in safety evaluation, those who satisfy the following conditions are excluded from efficacy evaluation and others are included in efficacy evaluation.

- i) patients from whom the information on efficacy before and after administration was not obtained.

3. Handling of patients

Unless otherwise specified, a patient recorded in a different CRF as a re-administered patient will be tabulated as one patient based on each CRF even if he/she is the same person. When tabulating the same patient as one patient, it should be clarified in “creation method” that tabulation is conducted for “each patient unit”.

4. Data Lock Point

(1) Data Lock Point

Date of starting survey: August 1, 2008

Data Lock Points (DLP) are shown below.

1st: September 30, 2008

2nd: March 31, 2009

3rd: September 30, 2009

4th: March 31, 2010

5th: March 31, 2011

6th: March 31, 2012

7th: March 31, 2013

8th: March 31, 2014

9th: March 31, 2015

10th: March 31, 2016

11th: March 31, 2017

12th: March 31, 2018, re-examination

13th: July 15, 2018, re-examination “(4) Safety analysis 10) Profile Table of serious adverse drug reactions,

11) Profile Table of adverse drug reactions not foreseeable from ‘Precautions’”

5. Tabulation and analysis at each DLP

(1) Patient composition diagram

<Analysis population>

Enrolled patients.

<Preparation method>

- 1) number of study sites
- 2) number of enrolled patients

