Prepare according to (Note) 1 to 7 in Attachment form 2 of PFSB/ELD Notification No. 1027004 of Director of Pharmaceutical Evaluation Division dated October 27, 2005. Attach a list of adverse drug reactions/infections by patient unit to the far right of this table.

Prepare a list of onset of adverse drug reactions according to administration category (initial administration, re-administration 1, re-administration 2, re-administration 3 onward) and treatment period (≤ 56 days, ≥ 57 days, unknown) in the same manner shown in Attachment form 2.

Accumulation and total section in (Note) 2

- The same site participating in Ph 2 and Ph 3 is counted once concerning the number of surveyed sites up to approval.
- A report submitted by the same site for the first and second reporting is counted once concerning

cumulative total section for the number of surveyed sites.

- A report submitted from the same site prior to approval and during a special drug use survey is counted once concerning a total section of a number of surveyed sites.

Number of occurrences of same adverse drug reactions/infections encountered in the same patient in (Note) 3

- In tabulation of SOC, several occurrences of the same SOC in a given patient is counted once.
- In tabulation of PT, several occurrences of the same PT in a given patient is counted once.

Infections in (Note) 7

- No infection was collected or reported by the time of obtaining approval.

Percentage (%) of number of onset (occurrence) of adverse drug reactions by types in (Note) 7

- Calculate percentage (%) for the number of patients by types (occurrences) to the second decimal place (round up to the second decimal place). The same is applied hereinafter unless otherwise stated.

3) List of occurrences of serious adverse events (Attachment form 10 of the notification of Director of Ministry of Health, Labour and Welfare)

<Analysis population>

Patients included in safety evaluation.

<Preparation method>

Prepare according to (Notes) 1 to 8 in Attachment form 10 of PFSB/ELD Notification No. 1027004 of Director of Pharmaceutical Evaluation Division dated October 27,2005. Present serious adverse events by patient unit at the far right of this table.Cumulative total and total section in (Note) 3

- The same site that participates in Ph 2 and Ph 3 studies is counted once concerning the number of surveyed sites up to approval.

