Number of target patients, number of patients with onset of adverse drug reactions, percentage (%), and number of occurrences of adverse drug reactions will be tabulated according to the patient demographics shown in Table (3). Presence or absence of adverse drug reactions will be tested according to the patient demographics to investigate the factor that affects safety.

Fisher’s exact test will be used for 2×2 contingency table for comparison of categorical data whereas Cochran-Armitage test will be used for $2 \times c$ contingency table for ordinal categorical data.

Table (3) Patient demographics

Item	Category
Sex	1) M, 2) F, 3) unknown
Age (years)	1) <65 years, 2) ≥ 65 years, 3) unknown
Weight (kg) ^{*1}	1) $<[\text{median}]$, 2) $\geq[\text{median}]$, 3) not measured (unknown)
Administration category	1) Initial administration, 2) re-administration
Dosing period (day)	1) ≤ 56 days, 2) ≥ 57 days, 3) unknown
Diagnosis name (osseous Paget’s disease)	1) monostotic, 2) polyostotic, 3) non-classifiable/ unknown
Morbid period ^{*2}	1) <1 year, 2) ≥ 1 and <5 years, 3) ≥ 5 years, 4) unknown
Complication	1) none, 2) present, 3) unknown

Item	Category
Details of complication ^{*3*4}	1) hypertension, 2) diabetes mellitus, 3) hepatic disease, 4) cardiac disease, 5) renal disease, 6) gastrointestinal disease, 7) other
Hypersensitivity	1) none, 2) present, 3) unknown
Details of hypersensitivity ^{*3}	1) drug, 2) food, 3) other, 4) unknown
History of drug therapy for osseous Paget's disease ^{*5}	1) none, 2) present, 3) unknown
Details of history of drug therapy for osseous Paget's disease ^{*3*5*6}	1) calcitonin preparation, 2) etidronate, 3) this drug (Benet, Actonel), 4) bisphosphonate other than this drug and etidronate, 5) unknown
Concomitant drugs	1) none, 2) present, 3) unknown
Details of concomitant drugs ^{*3*6}	1) osteoporosis agents, 2) anti-inflammatory analgesic, 3) cardiac medication, 4) CNS agents, 5) diabetes medication, 6) gastrointestinal medication, 7) other

*1: determine the calculated value for [median]

*2: morbid period starts on the “day of initial diagnosis of osseous Paget's disease” and ends on the “day of starting administration of this drug”.

*3: tabulate for each category (duplicate tabulation)

*4: classify disease names according to the MedDRA code

*5: tabulate prior therapies of osseous Paget's disease in the prior medication.

*6: classify according to the JAPIC Code (drug data file)

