6) Onset of adverse drug reactions <stratified analysis>

<Analysis population>

Patients included in safety evaluation.

<Preparation method>

The factors in “5) Onset of adverse drug reactions by factors” that show a significant difference ($p < 0.05$) concerning presence or absence of adverse drug reactions will be stratified according to the above Table (3), and each adverse drug reaction will be tabulated according to “2) List of onset of adverse drug reactions/infections (Attachment form 2 of the notification from director of MHLW)”. Factors will be compared between categories according to the types of adverse drug reaction (SOC [system organ class] of MedDRA).

7) Profile of adverse drug reactions after initial administration and re-administration in individual patient

<Analysis population>

Patients included in safety evaluation who receive re-administration irrespective of onset of adverse drug reactions.

<Preparation method>

Presence or absence of adverse drug reactions after the initial administration and re-administration, adverse drug reaction name (SOC, PT), seriousness, number of days up to onset of adverse drug reactions, and outcome

will be recorded for each patient. Patients with “presence” of adverse drug reactions will be shown first, followed by patients with “absence” of adverse drug reactions in the order of case number at the initial administration.

8) Summary of interval of re-administration

<Analysis population>

Patients included in safety evaluation who receive re-administration.

<Preparation method>

Summary statistics will be calculated for number of days from the date of completion of the previous administration (date of completion of initial administration in case of re-administration 1) up to the date of starting re-administration according to the number of re-administration.

Handling of re-administration and calculation of interval of re-administration are shown in section “(8) Other arrangements”.

9) Treatment compliance

<Analysis population>

Patients included in safety evaluation.

<Preparation method>

Number of patients and percentage will be shown for “drugs are taken as instructed (compliance of $\geq 90\%$)”, “sometimes forget taking drugs (compliance of $\geq 67\%$ and $< 90\%$)”, “taking drugs half the time (compliance of $\geq 25\%$ and $< 67\%$)”, “hardly taking the drug (compliance of $< 25\%$)”, and “unknown”.

10) Profile table of serious adverse drug reactions

<Analysis population>

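### The Fisher test of reaction rates between initial and repeat courses is open to selection into re-treatment, and no planned table shows that selection

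*SAP*

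**What the plan says.** SAP Version 4.1, section 5.(4)5), sets out a one-factor-at-a-time screen: "Presence or absence of adverse drug reactions will be tested according to the patient demographics to investigate the factor that affects safety". One of the factors in Table (3) is administration category, with levels "1) Initial administration, 2) re-administration". A two-level factor gives a 2×2 table, for which the section prescribes Fisher's exact test. Section 5.(4)6) then takes the factors "that show a significant difference ($p < 0.05$) concerning presence or absence of adverse drug reactions" into stratified tables and comparisons by system organ class.

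Three other provisions decide who is in each row:

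- SAP section 3 makes the course the unit of counting: "a patient recorded in a different CRF as a re-administered patient will be tabulated as one patient based on each CRF".
- Protocol section 5.(2) brings repeat courses in by re-enrolment: "A patient who was previously enrolled in this survey at the concerned site will be enrolled again when this drug is re-administered". It gives no criterion for who receives another course.
- SAP section 5.(4)2) asks the analyst to "Prepare a list of onset of adverse drug reactions according to administration category", by course number. Section 5.(4)4) does the same. Neither separates first courses by whether the patient was later re-treated.

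The only within-patient safety output is section 5.(4)7), which records "Presence or absence of adverse drug reactions after the initial administration and re-administration" for each re-treated patient. It is a listing without rates, and patients who were never re-treated are not in it. On the efficacy side, section 5.(5)1) does separate the first courses of patients later re-treated from those of patients who were not.

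**The concern.** The two rows are not comparable groups. The initial row contains everyone's first course, including patients who reacted and never took the drug again. The re-administration row contains only patients for whom another course was chosen. If a reaction makes another course less likely, and some patients are more prone to reactions than others, the repeat-course row is depleted of susceptible patients. Its rate then falls below the initial rate even when each person's risk is the same on every course.

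A separate defect is that a re-treated patient contributes to both rows, while Fisher's test assumes independent observations.

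The section presents the test as a search for factors that affect safety. A lower rate on repeat courses, with or without p<0.05, could therefore be read as reassurance about repeat treatment. The development experience described in Protocol section 1 is a single 8-week course in 12 patients, so there is little else in these documents to set against such a reading.

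**Working it through.** The plan gives no sample size, reaction rate or re-treatment rate, so there is no stated figure to reproduce. The check asks how far the repeat-course rate would move if the course had no effect at all. All inputs below are assumed.

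**Inputs**

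- m: reaction risk per course, the same on every course; 15%.
- ρ: within-patient correlation of reactions between courses; 0.1 to 0.5.
- r: chance of re-treatment after a first-course reaction, relative to no reaction; 0 to 0.5.

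**Formulas**

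- Repeat-course risk after no first-course reaction: A = m(1−ρ).
- Repeat-course risk after a first-course reaction: B = m(1−ρ) + ρ.
- Expected re-administration rate: [m·r·B + (1−m)·A] / [m·r + (1−m)].
- First-course rate among patients later re-treated: m·r / [m·r + (1−m)].

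**Central case, ρ = 0.3 and r = 1/3**

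- A = 0.15 × 0.7 = 0.105; B = 0.105 + 0.3 = 0.405.
- Weights: 0.15/3 = 0.05 for reactors, 0.85 for others, total 0.90.
- Re-administration rate: (0.05 × 0.405 + 0.85 × 0.105)/0.90 = 0.1095/0.90 = 12.2%.
- First-course rate in the same re-treated patients: 0.05/0.90 = 5.6%.

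| Case | All first courses | Re-administration | Ratio | First course, re-treated patients only |
|---|---|---|---|---|
| ρ = 0.1, r = 0.5 | 15% | 0.132375/0.925 = 14.3% | 0.95 | 0.075/0.925 = 8.1% |
| ρ = 0.3, r = 1/3 | 15% | 12.2% | 0.81 | 5.6% |
| ρ = 0.5, r = 0 | 15% | 7.5% | 0.50 | 0% |

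**When there is no bias.** With ρ = 0, A = B = m, so the rate is m whatever r is. With r = 1, the rate is m·B + (1−m)·A = m whatever ρ is. Both conditions are needed. The largest relative understatement is ρ itself, reached when r = 0.

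**Before/after comparison in re-treated patients.** The last column shows this is distorted the other way. In the central case it sets 5.6% against 12.2%, an apparent 2.2-fold rise with no change in risk.

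**What the p-value would do.** A simulation of 2,000 runs per scenario used a two-sided Fisher test at 0.05, an assumed 20% rate, re-treatment of 30% of patients without a reaction, and at most one repeat course each. The chance of a significant result falsely favouring re-administration was:

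| Scenario | 100 first courses | 200 first courses |
|---|---|---|
| ρ = 0, r = 1 | 1.5% | 2.0% |
| ρ = 0.3, r = 1 | 0.7% | 1.0% |
| ρ = 0.3, r = 0.5 | 2.1% | 4.6% |
| ρ = 0.3, r = 0 | 5.0% | 11.4% |
| ρ = 0.5, r = 0 | 13.7% | 32.5% |

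At 50 first courses it stayed below 2% in every scenario. The second line shows that, in this set-up, correlation without selection makes the test conservative. The simulation does not cover patients with several repeat courses, which the SAP allows for.

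**The case against.** A reader might infer that re-administration will look safer, as a built-in result of the comparison. The documents do not support that. No passage says that patients who reacted are re-treated less often, and the bias also needs reactions to recur within patients. In the mild case the shift is under one percentage point. Nor is the direction fixed by design: SAP section 5.(8)7) closes the previous case when re-administration starts. If that also ended adverse event collection (the text names only efficacy data), first courses in re-treated patients would be observed for less time, which pushes the other way.

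Three further points can be made for the plan:

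- Administration category is one of 15 rows in Table (3), and significance leads only to further tabulation and comparison by organ class, not to a stated conclusion on repeat courses. Repeat-course safety is not a named objective in Protocol section 1.
- With moderate inputs and about 100 first courses, the false-significance rate barely moves (2.1% against 1.5%).
- The listing in section 5.(4)7) covers every re-treated patient with or without a reaction. A paired table could be counted from it, and subtraction from the initial-course totals would give the patients never re-treated.

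These points limit the size and certainty of the concern. They do not remove it. The comparison is still unadjusted for who is re-treated, its rows still share patients, and a reader of the planned outputs would have to build the table that shows selection. That the counts are obtainable is a reason the correction is cheap.

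**Conclusion.** The concern holds in a conditional form. The comparison of all initial with all re-administration courses is confounded by selection into re-treatment, and the SAP plans no summary that shows the selection. Repeat courses may look safer than they are if reactors are re-treated less often and reactions recur within patients. Both are plausible; neither is documented.

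On an assumed 15% first-course rate, the understatement runs from 0.7 points (15% to 14.3%) through 2.8 points (to 12.2%) to 7.5 points (to 7.5%). The last requires correlation 0.5 and no reactor ever re-treated. The independence failure follows directly from the counting rule in SAP section 3 and needs no assumption beyond some patients being re-treated. It should not be read as inflating false positives, because the simulation with one repeat course per patient shows the opposite.

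**What to change.** In SAP section 5.(4)5), drop the Fisher p-value for administration category, so that this factor cannot trigger section 5.(4)6). Keep its counts and percentages as descriptive.

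Add one table, tabulated by patient unit, with n/N and exact 95% confidence intervals:

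- (a) the proportion later re-administered, by first-course reaction status (yes/no);
- (b) the reaction rate on re-administration 1, split by first-course reaction status, shown as the paired 2×2 table;
- the first-course reaction rate in patients never re-administered and in patients later re-administered.

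State beside it that the first-course rate in re-treated patients is itself lowered by selection (for example 5.6% against 12.2% on re-administration 1 under the central assumptions), so a before/after comparison in those patients must not be read as a course effect.

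The cost is SAP wording and one small table from data already collected. The table is descriptive, its numbers will be small (the row for re-treated reactors may be nearly empty), and the repeat-course rates still describe only patients chosen for re-treatment.

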A graph showing changes over time will be prepared for excess serum ALP up to Week 48 and percent change from baseline in each patient. A graph showing changes over time will be prepared to compare the initial administration in patients without re-administration and the initial administration in patients who received re-administration. Also, a graph showing changes over time will be prepared for re-administration 1 and subsequent administration in patients who received re-administration.

For the data at initial administration in patients who received re-administration, the measured data at each time point and percent change from baseline will be calculated, and summary statistics and two-sided 95% confidence interval will be shown. A paired t-test will be conducted for percent change and p-value will be shown for the test result. Also, changes in measured data at each time point and percent change from baseline will be shown for each patient.

For each of patients who receive re-administration, measured data at the initial administration and re-administration 1 and percent change from baseline will be compared in the same chart and the same graph.

2) Changes in excess serum ALP (subgroup analysis)

<Analysis population>

- i) Patients included in efficacy evaluation. However, a patient without baseline or post-administration data will be excluded.
- ii) Patients who received initial administration. However, it is not applicable to administration categories 1 and 2 because they are comparison with the initial administration.

<Preparation method>

Excess serum ALP will be stratified by the items shown in Table (4) to calculate the measured values at each time point and percent change from baseline. Summary statistics and two-sided 95% confidence interval will be conducted. Paired t-test will be conducted for percent change and p-value will be shown for the test result.

Table (4) Stratified categories

Item	Category
Sex	1) M, 2) F
Age	1) <65 years, 2) ≥65 years
Diagnosis name (osseous Paget's disease)	1) monostotic, 2) polyostotic
Administration category 1	1) initial, 2) re-administration
Administration category 2	1) initial, 2) re-administration 1, 3) re-administration 2 onward
Prior medication for osseous Paget's disease ^{*1*2}	1) No, 2) Yes
Prior administration of bisphosphonate product ^{*1*2}	1) No, 2) Yes
Concomitant medication for osseous Paget's disease ^{*2}	1) No, 2) Yes
Renal disease	1) No, 2) Yes
Hepatic disease	1) No, 2) Yes

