(7) List of summary of surveyed patients (Attachment form 3)

<Analysis population>

Patients from whom CRF is collected.

<Preparation method>

A list will be prepared to show case No., site name, founding organization/code, prefecture, patient initials, sex, age, inpatient/outpatient, reason for use (disease code, disease name), severity at baseline, complication (presence or absence, number listed, name), route of administration, maximum dose (day/dosage), mean dose (day/dosage), unit, number of daily administration (maximum), administration period, concomitant drug (drug code, typical name of drug, numbers listed), extent of efficacy, adverse drug reactions (organ code, adverse drug reaction code, adverse drug reaction name, presence or absence, number listed), outcome, CRF No. and dropout according to the CRF number.

(8) Other arrangements

1) Calculation method for age

Age at last birthday on the date of starting administration of this drug.

2) Date of starting administration of this drug

The earliest date of [details of treatment] recorded in CRF will be the date of starting administration of this drug.

3) Summary statistics

Summary statistics will be obtained for number of patients, mean, standard deviation, minimum, Q1, median, Q3, and maximum.

For display of digit, the original data of mean, standard deviation, Q1, median, Q3 will be rounded up to the first decimal place. The minimum and maximum will be shown in digit of original data.

4) Percent change

Percent change will be calculated as follows.

percent change = (measured value after administration – measured value at baseline)/measured value at baseline $\times 100$

5) Data at each evaluation time point

i) Acceptance range for each time point

The value measured at each point will be the data measured within the acceptable range shown in Table (5) when performing “(5) Efficacy analysis”.

ii) Data of Nth administration when administration was conducted for (N+1) times

Of the data of Nth administration recorded in CRF, the data obtained prior to the date of administration of (N+1) times will be used

Table (5) Acceptance range for each time point

Time point	Acceptable range	Standard
Baseline	-28 – 3 days	Day 1 (date of starting administration of this drug)
Week 4	4 – 42 days	28 days
Week 8	43 – 70 days	56 days
Week 12	71 – 126 days	84 days
Week 24	127 – 210 days	168 days
Week 36	211 – 294 days	252 days
Week 48	295 – 420 days	336 days
Final evaluation point	4 – 420 days	-

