In case several efficacy data exist for the same time point, proceed as shown below.

- 1) Select the data on the day closest to the standard date.
- 2) In case there are more than one data with the same number of days before or after the standard date, select the data after the standard date. However, select the data before the date of administration of this drug when time point is baseline.

6) Excess serum ALP

Excess serum ALP will be calculated as follows.

excess serum ALP = measured value of serum ALP - (maximum reference value + minimum reference

value)/2

However, denominator may become “0” when calculating percent change 4). When excess serum ALP becomes “0”, calculate the value as “0.01”.

7) Handling of patients who receive re-administration

Initial administration and re-administration will be judged based on “administration category” of CRF.

Whether or not the same patient has received re-administration will be judged based on the information on re-administration separately managed. When a patient has received several re-administrations, arrange them in a temporally order and number them re-administration 1 and 2 starting with the earliest date.

A previous case will be completed when re-administration is started. Accordingly, the efficacy data after the start of re-administration recorded in the prior CRF will not be used.

8) Calculation method for intervals of re-administration

Calculate number of days from the date of completion of previous administration (date of completion of administration for the initial administration in case of re-administration 1) up to the date of starting administration.

interval of re-administration = date of administration of this drug - date of completion of previous administration of this drug

9) Tests

Tests will be conducted by excluding “unknown”. p-value will be calculated up to the 4th decimal place (round up to the 4th decimal place).

10) Output of category “unknown”

In case category is “unknown” and target number of patients is 0, category “unknown” is not outputted.

**Benet 17.5 mg Tablets Special Drug Use Surveillance in Patients With
Osseous Paget's Disease (All-case Surveillance)**
**Actonel 17.5 mg Tablets Special Drug Use Surveillance in Patients With
Osseous Paget's Disease (All-case Surveillance)**
- 48-week surveillances-

Statistical Analysis Plan Version 4.0

Takeda Pharmaceutical Co., Ltd.

PPD

Change history

Version No.	Date of preparation/revision	Site/reason for change

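### The re-administration interval is summarised only where a further course began by 31 January 2016, so it is right-truncated: read as time to re-treatment it is too short, and it can show a spurious shortening with course number

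*SAP*

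**What the plan says.** All references are to SAP V4.1 unless stated.

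- **Population.** Section 5.(4)8) takes "Patients included in safety evaluation who receive re-administration". A course not followed by another does not enter.
- **Quantity.** Section 5.(4)8) states that "Summary statistics will be calculated for number of days from the date of completion of the previous administration" to the start of the next. Section 5.(8)8) defines "interval of re-administration = date of administration of this drug - date of completion of previous administration of this drug". There is no censoring term.
- **Display.** Results are given "according to the number of re-administration". Section 5.(8)3) fixes the statistics: "Summary statistics will be obtained for number of patients, mean, standard deviation, minimum, Q1, median, Q3, and maximum". No number at risk is shown and no time-to-event method is planned.
- **Cut-off.** Section 2.(2) iv) removes courses started outside the enrolment period, and its footnote explains: "The date of starting administration falls after the enrollment period of January 31, 2016".
- **Unit.** Section 3 counts each re-administration case report form (CRF) as its own patient unless stated otherwise. Protocol section 5.(2) i) makes each repeat course a new enrolment: "A patient who was previously enrolled in this survey at the concerned site will be enrolled again when this drug is re-administered". The cut-off therefore applies course by course.
- **Related graphs.** Section 5.(5)1) plans a graph to "compare the initial administration in patients without re-administration and the initial administration in patients who received re-administration" for excess serum ALP. Section 5.(5)4) has a similar graph for serum ALP.

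The SAP plans no test of trend across course numbers, gives no expected interval, and carries no caveat on this table.

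**The concern.** An interval is seen only if it ends before a fixed calendar date. Long intervals are less likely to close in time, so those tabulated lean towards short ones. A course ending on 1 January 2014 can contribute at most 760 days; one ending on 31 December 2014 at most 396. Courses still without a further course, which carry the information on long intervals, are dropped.

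The restriction tightens with course number. Re-administration 2 needs two intervals and two completed courses to fit before the same date, and re-administration 3 needs three of each. Even if true intervals were identical for every course, the expected tabulated values would fall from one course number to the next.

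Efficacy observation ends at Week 48 and the last efficacy window closes at day 420. The interval table is thus the planned output that looks furthest past that point, and it goes into the re-examination analysis. A reader could easily take its median as the usual time to re-treatment, or read across its rows as loss of effect with repeat courses.

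**Working it through.** **Inputs from the documents**

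- Survey start 1 August 2008 (SAP section 4); last eligible start 31 January 2016 (SAP section 2.(2) iv).
- Course length 56 days (8 weeks, Protocol section 3.(2)).
- Enrolment period stated as 7 years 6 months (Protocol section 6).

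**The plan's own figure.** From 1 August 2008 to 31 January 2016 is 90 months = 7 years 6 months, or 2,740 days counting both ends. This agrees with the protocol.

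**Assumptions, since the documents give none.** First courses start uniformly over the 2,740 days, or front-loaded (Beta(1,3)). Intervals have the same distribution after every course, either exponential or lognormal (sigma 0.6), with true median 0.5, 1, 2 or 3 years. Every patient is eventually re-treated.

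**Formula for re-administration 1.** A first course starting on day U gives an interval g only if U + 56 + g ≤ 2,740. With uniform U, the density of tabulated intervals is proportional to f(g) × (2,684 − g) for 0 < g < 2,684, where f is the true density. The second factor is the truncation: it weights short intervals up and long ones down.

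For an exponential interval with true median 1,096 days (true mean 1,581), integrating this gives a tabulated median of 533 days and a mean of about 673. The median shortfall is 1 − 533/1,096 = 51%.

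**Later courses, by simulation** (400,000 patients per scenario, uniform entry). Tabulated medians in days for re-administration 1 / 2 / 3:

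| True median | Lognormal | Exponential |
|---|---|---|
| 183 | 177 / 176 / 176 | 164 / 162 / 158 |
| 365 | 343 / 337 / 329 | 289 / 274 / 251 |
| 731 | 632 / 583 / 520 | 447 / 386 / 326 |
| 1,096 | 860 / 740 / 607 | 533 / 429 / 352 |

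Over both distributions and both entry patterns, the shortfall in the re-administration 1 median is about 0-10% (0.5 years), 1-21% (1 year), 6-39% (2 years) and 13-51% (3 years). The mean is below the true mean, and falls with course number, in all 16 constant-interval scenarios.

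**Does the shortening have to appear?** No.

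- If true intervals lengthen by 10% per course (lognormal, starting median 1 year, uniform entry), the tabulated medians rise: 343 / 367 / 385.
- In surveys of 50 to 200 patients with constant intervals, the mean for re-administration 2 lies below that for re-administration 1 in 51-57% of surveys (true median 0.5 years), 57-73% (1 year) and 72-91% (2 years).

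**Does a censored analysis cure it?** That depends on where it censors. Kaplan-Meier from completion of the course, censored at 31 January 2016:

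- lognormal, true 731 days: 732 after the first course and 732 after the second, against 632 and about 585 from the SAP summary;
- exponential, true 1,096 days: about 1,096 after the first course.

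In the second case, if courses without a further course are instead censored at last CRF contact, the Kaplan-Meier median is about 657 days (contact at Week 48) or 697 (day 420). With Week 48 contact, the estimated proportion re-treated at 3 years is about 75% against a true 50%. Past that contact, the only courses left at risk are those that go on to be re-administered, so most of the bias returns.

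**The case against.** The strongest objection is that the table claims nothing more than it shows. It sits under the safety analysis, describes intervals that occurred, and plans no comparison across courses. The survey's stated purpose runs to Week 48, and maintenance of effect is assessed by ALP up to that week. The interval also reflects prescribing as well as response. All of this stands. A reader might infer that the SAP understates how long the drug's effect lasts, but the SAP makes no durability claim, so the documents do not support that reading.

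A second tempting reading is that the intervals will shrink with each course. The working does not support it: shortening is the expected artefact when true intervals are constant, but genuine lengthening or small numbers can hide it, and at a median of about 6 months it is negligible.

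Third, every magnitude rests on assumed distributions. That also stands. With lognormal intervals around one year and uniform entry the re-administration 1 shortfall is about 6%. The direction is secure; the size is not.

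Fourth, the ALP graphs are descriptive and stop at Week 48. The survey runs to July 2017, 18 months past the end of enrolment, so late starters can still complete 48 weeks. What remains is that the group without re-administration mixes courses that did not need repeating with courses that had little time left in which to be repeated.

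None of this answers the central point: the table has no denominator and no warning, and its layout by course number invites the comparison it cannot support.

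**Conclusion.** The point holds in limited form. The intervals are right-truncated at 31 January 2016, or at the data lock point for reports locked before that date, where the truncation is stronger. As a description of closed intervals the table is right. As an estimate of time to re-treatment it is biased short, and it can show a spurious shortening with course number.

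The shortfall in the re-administration 1 median could be near zero or about half, depending on a true interval the documents do not give. The range of about 0-10% at 6 months to about 13-51% at 3 years assumes constant intervals, uniform or front-loaded entry, and eventual re-treatment of everyone. This is a secondary descriptive output with a known direction of bias and a cheap correction, so it should be changed, but it does not threaten the primary endpoint.

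**What to change.** 1. **Keep and label the table in 5.(4)8).** State that it describes re-administered courses only, is right-truncated at 31 January 2016 (or at the data lock point for earlier reports), and is not to be compared across course number.
2. **Add a Kaplan-Meier estimate** of time from completion of a course to the next re-administration, separately after initial administration and after re-administration 1. Put every completed course at risk, and show numbers at risk and 95% confidence intervals.
3. **Censor at 31 January 2016**, or at death or documented transfer if earlier. Do not censor at last recorded CRF contact, for the reason shown in the working.
4. **State the assumption** that a patient not enrolled again was not re-treated at another site. Protocol section 5.(2) requires re-enrolment at the same site, and the yearly signed confirmation supports completeness there, but neither covers other sites.
5. **For the ALP graphs in 5.(5)1) and 5.(5)4)**, add only a note that the group without re-administration includes courses with little time left for one. Limiting the graphs to courses with some minimum opportunity would be arbitrary and would discard data in a very rare disease.

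The cost is SAP wording plus one table and one figure, from start and completion dates and the re-administration link already held. Few patients may reach re-administration 1, so the second curve may be imprecise; its confidence intervals will show this.
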